6.2.2 On-Study/On-Interventions Evaluations/procedures

During the time the subject is in the Phase 1 unit, subjects' observations about the tolerability of the capsule administration will be recorded.

Admission Procedures (Day -1): Subjects will arrive at the Phase 1 unit on Day -1 and will undergo procedures:

- Medical history (to determine any changes since Screening)
- Concomitant medication review
- Infection screen
- Body temperature

- Vital signs (BP, HR)
- ECG (triplicate)
- Physical examination (must be performed by an Investigator), weight
- Neurological exam (must be performed by an Investigator)
- Safety laboratory tests (fasting, minimum 10 hours)
- Urine pregnancy test (females only)
- Breathalyzer
- Urine drug screen
- Randomize the subject. Only subjects whose admission procedures, including safety labs performed on Day -1, meet eligibility criteria will be randomized. Randomization may occur on morning of Day 1 if necessary (e.g., delay in safety laboratory test reporting).

Day 1 – Dosing: A light breakfast will be given prior to dosing.

- Pre-dose vital signs
- Pre-dose body temperature
- Final eligibility review. Only subjects who are confirmed 'eligible' by the Investigator will continue for dosing.
- Start telemetry monitoring approximately 30 min prior to dosing
- Pre-dose PK and ApoE blood sample
- Administer study drug to subject (Time 0)
- 0.25h PK sample
- 0.5h PK sample
- 1h ECG
- 1h vitals
- 1hr PK sample
- 2h ECG
- 2h vitals
- 2h PK sample
- 4h ECG
- 4h vitals
- 4h PK sample
- 8h PK sample
- 12h ECG
- 12h vitals

- 12h body temperature
- 12h PK sample
- Adverse event (AE) assessment (continual throughout Day 1)
- Concomitant medication review (continual throughout Day 1)

PK samples will be taken at the actual required time and the other evaluations should be scheduled around the PK sample.

Day 2: Day 2 times are anchored to the Day 1 dosing time (Time 0). Subjects will fast for a minimum of 10 hours. Water is allowed.

- Fasting safety laboratory tests (blood and urine)
- Light breakfast (subject may decline)
- ECG approximately 24h post-dose
- 24h PK sample
- 24h vital signs
- Physical exam (must be performed by an Investigator), weight
- Neurological exam (must be performed by an Investigator)
- 24h body temperature
- 36h PK sample
- 36h vital signs
- AE assessment (continual throughout Day 2)
- Concomitant medication review (continual throughout Day 2)

PK sample will be taken at the required time and the other evaluations should be scheduled around the PK sample.

Day 3: Discharge. Assessments and Procedures on Day 3 are anchored to the dosing time on Day 1 (Time 0).

- Vital signs
- Body temperature
- ECG
- Light breakfast (subject may decline)
- AE assessment
- Concomitant medication review

Day 7 Follow-up Visit: May be scheduled on Day 6, 7, or 8.

Subjects will fast for a minimum of 10 hours. Water is allowed. Subjects will undergo the following procedures:

- Fasting safety laboratory tests (blood and urine)
- ECG
- Vital signs
- Body temperature
- Physical examination (must be performed by an Investigator), weight
- AE assessment
- Concomitant medication review

Treatment-related AEs ongoing at the Follow-up assessment will be followed until resolution or deemed stable, where feasible. Any Follow-up safety laboratory tests that are deemed clinically significant by the Investigator will be repeated and followed until stabilization at the discretion of the Investigator/Sponsor.

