Interventions and Duration	
Subjects will be screened in the 28 days prior to inpatient admission. Subjects will be admitted to the inpatient clinic on the day prior to dosing (Day -1) and will remain in the unit until discharge on Day 3. A follow-up visit will be done on Day 7. A single dose of study drug or placebo will be administered on Day 1.
 
40 healthy adult subjects will be assigned to one of 5 dose cohorts (8 subjects each). The starting dose (10 mg) cohort 1 will include male and female subjects; cohorts 2 – 5 will include only female subjects. Within each cohort, 8 subjects will be randomized to receive MW151 or placebo in the ratio 6:2. According to the dosing scheme each subject will receive a single dose of MW151 or placebo under fasted conditions.
 
1. Starting dose: Dose1 (10 mg)2. Dose2 (20 mg)3. Dose3 (40 mg)4. Dose4 (80 mg)5. Dose5 (160 mg) 
As a safety consideration two sentinel subjects in each cohort will be administered MW151 or placebo in a 1:1 ratio.

-----------------------------------	--

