5.3.1 Required Concomitant Medications/Interventions

Subjects are required to fast for at least 10 hours before all safety laboratory samples. Subjects are allowed water ad libitum. Breakfast may be given on Day 1 before dosing; other meals and snacks may be served at the study site's standard times. The study site will provide subjects with standard meals and snacks while in the Phase 1 unit. The daily menu information will be included in the final clinical report as an appendix.

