- Screening (all except creatine kinase, amylase, lipase)
- Day -1
- Day 2
- Day 7

(8) A 12-lead ECG will be performed (after lying quietly for 5 minutes). Triplicate tracings (3x) will be taken at Day -1 only and will serve as the Baseline (pre-dose measurement). ECGs will be performed at the following time points.

- Screening
- Day -1
- Day 1: approximately 1h, 2h, 4h, and 12h post-dose
- Day 2: approximately 24h post-dose
- Day 3
- Day 7

Subjects will be monitored on telemetry from approximately 30 min prior to dosing through the 4 hour post-dose ECG.

(9) Vital signs will include BP and HR. At each time point where vital signs are measured, heart rate and blood pressure will first be checked in the supine position and then in the standing position with at least 2 minutes between the supine and standing measurements. Vitals will be performed at the following time-points:

- Screening
- Day -1
- Day 1: Pre-dose and at 1h, 2h, 4h, and 12h post-dose

- Day 2: approximately 24h and 36h post-dose
- Day 3
- Day 7

(10) PK samples will be taken at the following time-points, anchored to the start of dosing.

- Day 1: Pre-dose, and 0.25h, 0.5h, 1h, 2h, 4h, 8h, 12h post-dose
- Day 2: 24h and 36h post-dose

(11) Randomization is expected to occur on D-1, but if there are delays in receiving prequalification safety labs randomization may occur on D1 prior to dosing.

(12) Dosing will be by oral capsule administration, on day 1.

(13) ApoE will be collected pre-dose on Day 1

6.2 **Timing of Study Activities**

Order of Tests: When several assessments are required at the same time point, evaluations should be completed in the following order, with **PK sample collection at the required time**. As such, it is understood that ECGs and vital sign measurements may be performed before the actual time point to allow for rest times and procedures:

- Fasting safety laboratory sample
- ECG (supine)
- Vital signs
- PK sample
 - Allowable Windows:
 - PK window for 15min, 30min and 1h post-dose samples: \pm 5 minutes
 - PK window for \geq 2h post-dose samples: \pm 10 minutes
- Day 7 Follow-up visit: \pm 1 day

6.2.1 **Screening/Pre-Randomization Evaluations/procedures**

Screening: Having given written informed consent, each subject will be required to undergo a medical screen within 28 days of Day 1. The subject will undergo the following procedures:

- Demographics
- Medical history
- Concomitant medication review
- Columbia Suicide Severity Rating Scale (C-SSRS)

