Vital Signs (BP, HR, Body Temperature): Summary statistics for BP and HR and change from baseline (predose) summaries will be presented for each treatment group and dose level where applicable. Summary statistics will include number of subjects, mean, standard deviation, minimum, and maximum. Listings for all vital signs will be presented.

Post-dose clinically notable vital signs will be listed and summarized by treatment and dose. Notable abnormalities are indicated in **Table 5** below:

Table 5: Criteria for Clinically Notable Vital Sign Abnormalities

Parameter	High Threshold	Low Threshold
Systolic BP (supine)	> 30 mmHg increase from baseline	> 30 mmHg decrease from baseline
Diastolic BP (supine)	> 20 mmHg increase from baseline	> 30 mmHg decrease from baseline
Heart Rate	> 120 bpm and an increase in HR of ≥ 15 bpm from baseline	< 40 bpm and a decrease in HR of ≥ 15 bpm from baseline
Body Temperature	> 39.0°C ($> 102.2^{\circ}\text{F}$)	< 35.0°C ($< 95.0^{\circ}\text{F}$)

12-Lead ECG: ECG results from the central reader will be used in the analysis. Shift tables summarizing the numbers of subjects shifting from normal pre-dose values to abnormal post-dose values will also be presented. Numeric ECG data will be summarized by treatment group and dose level and mean summary tables, including change from baseline will be presented.

The ECG results will be listed by treatment group and dose level.

Post-dose clinically notable ECGs will be listed and summarized by treatment and dose. Notable abnormalities are indicated in [Table 6](#) below:

Table 6: Criteria for Clinically Notable ECG Abnormalities

Parameter	High Threshold	Low Threshold
PR interval	PR ≥ 220 ms	PR ≤ 120 ms
QRS duration	QRS duration ≥ 120 ms and an increase of ≥ 20 ms from baseline	-
QT interval	QT interval > 500 ms	-
QTcF interval	Men: QTcF interval ≥ 450 ms and an increase of ≥ 60 ms from baseline OR QTcF interval > 500 ms Women: QTcF interval ≥ 470 ms and an increase of ≥ 60 ms from baseline OR QTcF interval > 500 ms	-

Pharmacokinetic Analysis: The plasma concentrations of MW151 will be determined, and used to estimate appropriate PK parameters including C_{max} , T_{max} , AUC, $T_{1/2}$ and K_{el} by non- compartmental analysis. The PK analysis population will include all subjects who received the active study drug and who have sufficient MW151 plasma concentrations to calculate at least 1 PK parameter.

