PK parameters will be listed for each individual subject and summarized for each dose level; the summary will consist of number of subjects, arithmetic mean, standard deviation, and geometric mean, coefficient of variation, minimum, median, and maximum. Profiles for each subject will be presented graphically. Additionally, a mean profile will be presented by treatment group and dose level.

The PK analysis will be conducted at a facility selected by the Sponsor. PK data will be provided to the Sponsor for inclusion into the final clinical study report.

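### The Synopsis has subjects dosed fasted, Section 6.2.2 gives them breakfast first, Section 5.3.1 makes that breakfast optional, and nothing reconciles the three

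*Combined protocol and SAP*

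**What the plan says.** Three current protocol statements deal with food before the Day 1 dose.

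- Synopsis, Interventions and Duration: "each subject will receive a single dose of MW151 or placebo under fasted conditions".
- Section 6.2.2, opening line of the Day 1 procedure: "A light breakfast will be given prior to dosing".
- Section 5.3.1: "Breakfast may be given on Day 1 before dosing".

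The only fast with a stated length is also in Section 5.3.1: "Subjects are required to fast for at least 10 hours before all safety laboratory samples". It concerns laboratory sampling, not dosing. The dosing footnote to the Schedule of Activities (Section 6.1, footnote 12) reads "Dosing will be by oral capsule administration, on day 1" and is silent on food. So are Section 5.1 and the dosing description in SAP Section 2.0.

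The PK profile is the secondary objective (Section 1.2). Under Section 9.1, plasma concentrations are "used to estimate appropriate PK parameters including" Cmax, Tmax and AUC, and "PK parameters will be listed for each individual subject and summarized for each dose level". Section 3 adds an interim PK analysis after Cohort 2.

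**The concern.** Fasted dosing and dosing after breakfast are opposite conditions for the same subjects on the same morning. Staff cannot satisfy both the Synopsis and Section 6.2.2, so whichever they follow departs from one of them.

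At stake is the condition under which the first human Cmax, Tmax and AUC are measured. For an oral drug, a PK profile needs a stated prandial condition before it can be interpreted or compared with later studies. Two consequences are possible. If everyone is treated alike but contrary to the Synopsis, the data are sound and the label is wrong. If practice differs between subjects or cohorts, any food effect is mixed with within-cohort spread or with dose, and each dose level has only six treated subjects.

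**Working it through.** No figure in the plan needs reproducing here. The check sets the texts side by side, counts who is affected, and asks what each reading would do to the PK comparison.

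**1. The texts compared**

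| Place | Food before the Day 1 dose |
|---|---|
| Synopsis | Fasted, every subject |
| Section 6.2.2, Day 1 | Light breakfast, stated as definite |
| Section 5.3.1 | Breakfast permitted, not required |
| Section 6.1, footnote 12 | Silent |
| SAP Section 2.0 | Silent |

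Section 5.3.1 is compatible with 6.2.2, but it neither confirms that everyone eats nor mentions the Synopsis condition. Section 6.2.2 lets subjects decline breakfast on Days 2 and 3 and says nothing of the kind for Day 1, so its Day 1 breakfast reads as a firm instruction.

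**2. Can the 10-hour fast settle it?** Safety laboratory samples are scheduled at Screening, Day -1, Day 2 and Day 7 (Section 6.1, footnote 7). None falls on Day 1, so the laboratory fast does not reach the dose.

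**3. Can 'fasted' mean some hours after a light breakfast?** Only if a section defined it so or fixed the interval. None does. The sole timing in 6.2.2 is that the meal precedes the dose.

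**4. Can another document settle it?** A separate PK analysis plan is foreseen (protocol Section 9.1; SAP Section 9.0) and was not available for this review. Section 9.1 requires sign-off only before database lock. That plan can describe the condition used but cannot be relied on to instruct staff at dosing.

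**5. Who is affected.** 5 cohorts × 8 = 40 planned subjects; 5 cohorts × 6 = 30 on MW151 and expected to contribute PK.

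**6. What each practice would do.** Suppose, for illustration, that eating multiplies a PK parameter by a common factor f. Let q be the fraction of a cohort's treated subjects who ate. The ratio of geometric means between cohorts B and A is then

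observed ratio = true ratio × f^(qB − qA).

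- Everyone fed (qA = qB = 1): f^0 = 1. Dose levels remain comparable, the values are fed-state, and the Synopsis is wrong.
- Everyone fasted (qA = qB = 0): f^0 = 1. Dose levels remain comparable, and 6.2.2 has been departed from throughout.
- One cohort fasted, the other fed: the ratio is distorted by the full factor f.
- One of six treated subjects in a cohort eating differently from the rest: that cohort's geometric mean moves by f^(1/6) or its inverse.

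The documents give no value for f. It could equal 1, in which case every line above is harmless. SAP Section 11.0 also says there is no prior basis for estimating human PK variability, so no numerical effect is claimed.

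**The case against.** The strongest reply is that the practical risk is small. Both body sections that mention Day 1 food place or allow breakfast before the dose; only one Synopsis phrase says otherwise, and a unit normally works from the visit-by-visit procedure. There is one inpatient site with standardized meals, and dosing is directly observed (Section 5.4). Section 5.3.1 also puts the daily menus in an appendix to the final report. The PK summary is descriptive, and these documents contain no PK-based escalation rule. All of this stands. It makes uniform fed dosing the likeliest outcome and mixed practice less likely. It does not remove the contradiction, and the menus need not show who ate or how long before the dose.

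Three stronger readings are tempting and not supported.

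- *The dose comparison is confounded.* A reader might infer this from the conflict. It would need practice to vary and a food effect to exist; the documents show neither.
- *Breakfast ends at least 30 minutes before dosing.* A reader might infer this because 6.2.2 also says "Start telemetry monitoring approximately 30 min prior to dosing". The breakfast sentence stands in the Day 1 opening line, outside the bulleted procedures, and the bullets are not strictly chronological: assessments running all day come last. No bound follows.
- *Safety is compromised, or safety is untouched.* A reader might infer either. Section 2.3.1 links QTc prolongation in dogs to peak plasma concentration, and ECGs are analysed as safety data, so a food effect on Cmax cannot be dismissed as irrelevant. Equally, the halting criteria in Section 8.1 rest on adverse events and clinical judgement, and nothing shows that food changes human exposure. No effect on safety is shown or excluded.

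**Conclusion.** The contradiction is real, and confidence in it is high because it rests on the text alone. It should be fixed because it is a dosing instruction that cannot be followed as written.

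Confidence in any harm is much lower. The expected result is a consistent fed-state PK data set that the Synopsis describes as fasted. That expectation assumes staff follow 6.2.2 for all subjects, which the setting makes likely but does not guarantee. Mixing of prandial state with dose is a possibility, not a finding. The instruction covers every planned subject; the size of any PK effect is unknown and possibly nil.

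**What to change.** State one prandial condition in identical words in the Synopsis, Section 5.3.1 and Section 6.2.2, for all subjects and cohorts. The choice is the sponsor's.

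- Smallest change: correct the Synopsis to match 6.2.2, and change 'may' to 'will' for the Day 1 breakfast in 5.3.1.
- Alternative: remove the pre-dose breakfast from 5.3.1 and 6.2.2 and state how long subjects fast before dosing.

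In either case, report PK under the condition actually used. If any cohort has already been dosed, this last step still resolves the ambiguity for readers.

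Two optional additions go beyond removing the contradiction: a fixed meal-to-dose interval, and a recorded Day 1 meal time for each subject.

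The cost is a wording amendment with Sponsor and IRB approval (Sections 6.3.2 and 9.2.3) and, if meal time is recorded, one extra data item per subject. No extra subjects, visits or samples are needed.

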6.2.3 Study Medication/Intervention Discontinuation Evaluations/Procedures

Sufficient numbers of subjects will be enrolled into the Screening Phase to ensure 8 eligible subjects are available for dosing in each dosing group.

Subjects may withdraw from the study for any reason at any time. The Investigator may discontinue subjects from the study in order to protect subject safety and/or if the subject is unwilling or unable to comply with required study procedures. Subjects may also be withdrawn from the study if the Sponsor or Regulatory Authorities terminate the study prior to its planned end date.

Should a dosed subject terminate prematurely from the residential phase of the study, the Investigator will make every effort to complete the Early Termination evaluations, which consist of the procedures scheduled for Day 3 before a subject is discharged and a physical examination. A PK sample may be drawn at the discretion of the Investigator.

Subjects discontinuing after randomization but before dosing may be replaced. Subjects discontinuing after dosing may be replaced. If a dosed subject is withdrawn or withdraws due to safety reasons, they will not be replaced. Decisions to replace dosed subjects will be made on a case-by-case basis depending on the timing of the discontinuation.

6.2.4 Pregnancy

Women who are pregnant at screening or on Day -1 testing will not be allowed to enter into the study. The likelihood of a female subject becoming pregnant while receiving MW151 is highly unlikely because of the requirement for a negative pregnancy test on Day -1 and the requirement that an acceptable barrier form of birth control be used during the study. Therefore, a pregnancy consent form will not be needed and no additional evaluations will take place.

6.3 SPECIAL INSTRUCTIONS AND DEFINITIONS OF EVALUATIONS

6.3.1 Informed Consent

Written informed consent will be obtained from each participant by a study team member authorized to obtain consent. Informed consent will be obtained before any study-specific procedures or assessments are performed and after the aims, methods, anticipated benefits, and potential hazards are explained. The participant's willingness to participate in the study will be documented in writing in a consent form, approved by the IRB, which will be signed by the participant with the date of that signature indicated. The investigator will keep the original consent forms and copies will be given to the participants. It will also be explained to the participants that they are free to refuse entry into the study and free to withdraw from the study at any time without prejudice to future treatment. Written and/or oral information about the study in a language understandable by the participant will be given to all participants. HIPAA guidelines for confidentiality and the principles of medical ethics will be adhered to during the study.

6.3.2 Protocol Amendments and Study Termination

All revisions and/or amendments to this protocol must be approved in writing by the Sponsor and the IRB. The Investigator will not make any changes to the conduct of the study or the protocol without first obtaining written approval from the Sponsor and the IRB, except where necessary to eliminate an apparent immediate hazard to a study subject.

The Sponsor reserves the right to discontinue the study at a clinical study site(s) for safety or administrative reasons at any time. Should the study be terminated and/or the clinical study site closed for any reason, all documentation and study medication pertaining to the study must be returned to the Sponsor or its representative.

6.3.3 Pharmacokinetic Studies

Samples will be taken as described in [Sections 6.1](#) and [6.2](#). Blood samples can be drawn via direct venipuncture or an indwelling catheter may be used. Catheters will be flushed with saline before and after sampling. Heparin flushing is not permitted.

If using a catheter, after the saline flush, withdraw and discard approximately 1.5 mL of blood before obtaining the sample to avoid sample dilution. Next, take 5 mL of blood into a pre-labeled plasma collection tube. Refer to the Laboratory Manual for the specific type of plasma collection tube to be used and for detailed sample processing instructions.

To avoid cross contamination of MW151 and placebo samples, separation of plasma aliquots should be done for one subject at a time, changing gloves between subject samples.

Following processing, plasma will be split into two aliquots. The 1st tube will be sent for PK analysis, and the 2nd tube will be a PK retention sample. Until samples are shipped to the analytical facility they will be frozen at -70°C (+ 10°C). Samples will be sent frozen on sufficient dry ice to maintain frozen conditions for at least 72 hours. The Sponsor will provide direction regarding the timing of sample shipment and sample destruction as applicable.

6.3.4 Laboratory Studies

Laboratory samples will be taken at the time points described in [Section 6.1](#) and [Section 6.2.2](#). Samples will be labelled per laboratory specifications. The parameters listed in [Table 4](#) will be evaluated:

Table 4: Laboratory Tests

Hematology & Coagulation	Biochemistry	Urinalysis

 • Hemoglobin (Hb) • Hematocrit • Red blood cell count (RBC) • White blood cell count (WBC) • Mean cell Hb • Mean cell Hb concentration • Mean cell volume • Platelet count • Red Cell Distribution Width • % Basophils • % Eosinophils • % Lymphocytes • % Monocytes • % Neutrophils • Basophil count • Eosinophil count • Lymphocyte count • Monocyte count • Neutrophil count • Reticulocyte count • Activated partial thromboplastin time 	
 • Pregnancy Test (serum) • Follicle Stimulating Hormone • Sodium • Potassium • Calcium • Chloride • Phosphorus • Glucose • Total protein • Albumin • Creatinine • Amylase • Lipase • BUN • Bilirubin • ALP • AST • ALT • GGT • Creatine kinase • Total cholesterol • High density lipoprotein • Low density lipoprotein • Triglycerides 	
 • pH • Protein • Blood • Ketones • Glucose • Bilirubin • Nitrite • Specific gravity • Leucocytes 
If any abnormal value is observed on the urine dipstick test the sample should be further analyzed with urine microscopy:
 
 • WBC • RBC • Cellular casts • Granular casts • Hyaline casts

Genetic Testing	Drugs of Abuse (Urine) & Alcohol Testing	Serology Screen & TB Test
Apolipoprotein E	Cannabinoids Amphetamines Barbiturates Cocaine Opiates Benzodiazepines Phencyclidine Methadone Alcohol (ethanol)	Hepatitis B surface antigen Hepatitis C antibody HIV 1 & 2 antibodies Quantiferon TB Gold PLUS test

All values falling outside the laboratory normal range must be assessed for clinical significance.

